Thank you so much for your interest in our research. Please don't hesitate to contact us if you have any questions as you are filling out the survey. Have a great day!

Step 2: Review Screen

1. Check Survey Monkey for screen if it is your folder day
 - a. **Screen:**
https://www.surveymonkey.com/collect/?sm=rdfeMF4WmHZAwsLTT7mCDtxNhHMMd_2B_2BgRbeMWz3R_2Bz1Oyx9qXYlgLMacO5axHRWS
 - b. Click on **Exports** on the left hand side of the screen
 - c. Click **Export All** and choose **All Responses Data** in the dropdown
 - d. Select .XLS for format
 - e. In the **Cells**: dropdown menu choose "Numerical Value"
 - f. Click the **Export** button
 - g. When it finishes loading, click the drop down arrow and select download.
 - h. Open the zip file
 - i. Go to excel folder and select Sheet_1
 - j. Copy and paste answers into 'PatientScreen.ALL' tab in the [Eligibility Screen DB](#)
 - k. Score PHQ-9 to ensure patient meets criteria for depression (Total score = 11+). See column AQ in 'PatientScreen.ALL' tab in the [Eligibility Screen DB](#) for total score.
 - l. Determine if patient is eligible or not.
 - i. If eligible: copy/paste information into 'Eligible.Patients' tab in [Eligibility Screen DB](#)
 - ii. If unsure: consult with [name] on how to follow up
 - m. Review screen for any skipped questions or those you need to follow-up on. Note these as follow-up items during phone call.
 - n. Review 'Patient Referrals Received' tab in the [Eligibility Screen DB](#)
 - i. If they are not listed in the list, look to see what clinic they are from in the screen to ensure they are being treated at one of our participating clinics
 - o. **Make note if they gave us permission to contact their therapist and/or clinic**

If patient is ineligible:

1. Send ineligible email
2. If we have permission to contact therapist and/or clinic, call to inform the clinic that patient is ineligible to participate

If patient passes screen or unsure:

1. Flag any questions and consult with [name] on how to answer.

WILLOW Full RCT Patient Protocol

2. Create a cover sheet for the patient with contact information and keep notes of all interaction with the patient in the log.
3. Call and Email Patient for clarification of eligibility and/or Informed Consent

Voicemail Script if Eligible:

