## WILLOW Full RCT Patient Protocol

standard therapy and computer-assisted therapy aided by our newly developed software called WILLOW. If you decide to participate in this study, you will be asked to meet with a therapist for 12 weeks. Your therapist has already been assigned to one of the two study conditions [let them know what condition they were assigned], which means you are also in the [standard care, WILLOW] condition with them.

**<<for RA: if not yet assigned to therapist, describe both conditions. If assigned to therapist and we know their condition, describe only the condition they are assigned to unless they want to hear about both conditions.>>**

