### **Ask them the date for the next session and record in coversheet**

- If you're able to complete your first set of surveys today [before next session], then I'll go ahead and send you that link to the quick survey for you to do.
- Now, the next three times we'll ask for you to complete surveys will be at Weeks 4, 8, and 12 during your participation. These will take between 45-60 minutes to complete and will involve a 10-15 minute phone call with a member of our research team and then an online survey that will take about 30 minutes answering questions about your mood, your satisfaction with the treatment you are receiving, and questions about your experience with your therapy and therapist.

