PracticeGround: Transforming Training and Delivery of Mental Health EBPs

NCT02314624 | Statistical Analysis Plan | February 8, 2020

Analysis Strategy

We conducted all analysis in IBM SPSS V19. We used the Generalized Linear Model to examine the between-condition change over time on study outcomes. The effects of primary interest were those reflecting the effects of WILLOW. For outcomes measured at baseline and follow-up points, that was the Time X Condition effects (measuring between-condition change from baseline). For outcomes measured only at follow-up points (e.g., therapeutic alliance and use of evidence-based therapy tasks), that was the Condition effects since they would represent average between-condition differences during the time patients received services. As previously mentioned, providers completed questionnaires for each study patient they treated. Hence, the provider sample size reflects the number of patients they answered about, not the number of providers. Several providers participated in the study concurrently with multiple patients. Patients were included in the analyses only if they attended five or more sessions with a participant provider.

Preliminary analyses provided important information guiding our strategy. First, we found no statistically significant differences between conditions on baseline measures. Second, we computed the design effects due to this nested design to determine the extent to which the intraclass correlation due to clustering and size of the cluster affected the analyses. Design effects ranged up to 1.8. Because all were under 2.0, we did not adjust analyses to account for clustering effects (Muthén & Satorra, 1995). For providers meeting participating in both studies, we used their Study 1 data for outcomes except for outcomes measured only in Study 2. For those outcomes, we used their Study 2 data.

References

Muthén, B.O. & Satorra, A. (1995). Complex sample data in structural equation modeling. *Sociological Methodology*, 25, 267-316. doi: 10.2307/271070

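### The SAP relies on non-significant baseline tests and names no baseline covariate; adjusting for baseline would protect against chance imbalance and cost no precision in large samples, but the documents do not fix the size of the gain.

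*SAP*

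**What the plan says.** The SAP's Analysis Strategy names its model in one sentence: "We used the Generalized Linear Model to examine the between-condition change over time on study outcomes". For outcomes measured at baseline and follow-up, the effect of interest is stated thus: "that was the Time X Condition effects (measuring between-condition change from baseline". For outcomes measured only at follow-up, such as therapeutic alliance and use of evidence-based tasks, "that was the Condition effects since they would represent average between-condition differences during the time patients received services". The next paragraph opens with "Preliminary analyses provided important information guiding our strategy", and the first item of that information is that "we found no statistically significant differences between conditions on baseline measures". No covariate of any kind is named.

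Pre-treatment data exist. In the Patient Protocol, Step 2 (Review Screen), staff are told: "Score PHQ-9 to ensure patient meets criteria for depression (Total score = 11" or more. Step 3 (Patient Informed Consent Call) sends each patient a first survey set after the call, and "the next three times we'll ask for you to complete surveys will be at Weeks 4, 8, and 12". The same step has staff tell the patient, where it applies, "Your therapist has already been assigned to one of the two study conditions", and say which one, before those first surveys are completed.

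**The concern.** Two things look weak. First, a non-significant baseline test is treated as useful information about balance. In a trial of modest size such a test will usually miss an imbalance large enough to matter.

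Second, baseline is used either in full, by subtraction, or not at all. When an imbalance arises by chance, the follow-up difference it produces depends on the regression of follow-up on baseline. Subtraction removes the whole baseline difference whatever that regression is. A plain follow-up comparison removes none of it. Conditioning on baseline removes the amount that the data support. At stake are the precision of the WILLOW comparison and its exposure to imbalances too small to reach significance.

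**Working it through.** **Inputs.** From the documents: follow-up at Weeks 4, 8 and 12; the two effects named in the SAP; a screening PHQ-9; design effects up to 1.8. The documents state no sample size, SD, correlation or power, so there is no figure of theirs to reproduce. Assumed: 30 to 40 patients per arm; r from 0.3 to 0.7, equal between all occasions; k = baseline SD / follow-up SD from 0.5 to 1; follow-up SD set to 1 and equal across the three weeks; complete data; independent patients.

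**1. What the baseline test can show.** For a true imbalance of 0.3 SD, the noncentrality is 0.3√(n/2), which is 1.16 at n = 30 per arm and 1.34 at n = 40. Two-sided 5% power by the noncentral t is 0.208 and 0.263, so the imbalance is missed 79% and 74% of the time. Clustering makes this worse. At an assumed 50 per arm the power is 32%, and 20% if a design effect of 1.8 applies to the baseline measure.

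**2. Precision, one follow-up.** The variance factors are:
- change: 1 + k² − 2kr
- adjusted for baseline: 1 − r²
- difference: (k − r)², which is never negative and is zero when k = r.

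**3. Precision, mean of three follow-ups.** The SAP does not say that this is its contrast. Replace the leading 1 by (1 + 2r)/3 in both factors. The difference is again (k − r)².

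**4. Chance imbalance.** If baseline differs by D baseline SDs, the expected follow-up difference with no treatment effect is rD. Change subtracts kD, so its error is |k − r|D in follow-up SDs. The adjusted estimate has no such conditional error in large samples.

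| r | k | Ratio, one follow-up | Ratio, mean of three | Error when D = 0.3 |
|---|---|---|---|---|
| 0.3 | 1 | 1.40/0.91 = 1.54 | 0.933/0.443 = 2.11 | 0.21 |
| 0.3 | 0.7 | 1.07/0.91 = 1.18 | 0.603/0.443 = 1.36 | 0.12 |
| 0.3 | 0.5 | 0.95/0.91 = 1.04 | 0.483/0.443 = 1.09 | 0.06 |
| 0.5 | 1 | 1.00/0.75 = 1.33 | 0.667/0.417 = 1.60 | 0.15 |
| 0.5 | 0.7 | 0.79/0.75 = 1.05 | 0.457/0.417 = 1.10 | 0.06 |
| 0.5 | 0.5 | 0.75/0.75 = 1.00 | 0.417/0.417 = 1.00 | 0.00 |
| 0.7 | 1 | 0.60/0.51 = 1.18 | 0.40/0.31 = 1.29 | 0.09 |
| 0.7 | 0.7 | 0.51/0.51 = 1.00 | 0.31/0.31 = 1.00 | 0.00 |
| 0.7 | 0.5 | 0.55/0.51 = 1.08 | 0.35/0.31 = 1.13 | 0.06 |

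A simulation at k = 1, r = 0.5 (50 per arm, 10,000 runs) agreed. The slope of the estimate on the baseline difference was −0.50 for change, +0.50 for an unadjusted follow-up comparison and 0.00 for the adjusted analysis.

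**5. In terms of power.** If the adjusted analysis has 80% power, the change analysis has Φ(2.80/√V − 1.96), with V the variance ratio. For the mean of three at r = 0.5, this is 60% at V = 1.60 (k = 1) and 76% at V = 1.10 (k = 0.7).

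**6. Follow-up-only outcomes.** Adjusting for a screening PHQ-9 that correlates c with the outcome leaves a variance factor of 1 − c²: 0.99, 0.96 and 0.91 at c = 0.1, 0.2 and 0.3. The reduction is 1 to 9%.

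**The case against.** Several points on the other side have force.

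- **Equal SDs.** A reader might infer that subtracting baseline loses precision at any correlation below 1. That is true only when the two SDs are equal. When k = r nothing is lost. Selecting patients on a PHQ-9 cut-off narrows the spread near entry, so k below 1 is plausible, and that pulls the loss down. This stands, and it is why k is varied above.
- **The contrast.** Time by Condition could be a multi-degree-of-freedom interaction or a slope. The mean-of-three figures are illustrative only. This also stands.
- **Silence.** The SAP lists effects of interest and does not say that covariates were excluded. A model that constrained the baseline means to be equal would behave like an adjusted one. But a plan that names its effects and its preliminary checks and no adjustment can fairly be read as unadjusted, and one sentence would settle the matter. A reader might also infer that covariates were left out because the baseline tests were non-significant. The SAP says only that those tests helped to guide strategy.
- **Non-equivalent arms.** Therapists are randomised and patients join afterwards. WILLOW therapists may recruit their own patients (Therapist Protocol, Step 7), patients may learn their arm before the baseline surveys, and only those with five or more sessions are analysed. If the arms differ systematically, neither change scores nor regression on baseline is unbiased in general. This limits the claim about bias, but it does not favour change scores.
- **Timing.** The SAP is written in the past tense. Replacing the primary analysis now would be a post hoc switch. Reporting both results, with the added one labelled, meets this.

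**Conclusion.** The point holds in a limited form. Non-significant baseline tests are not a sound basis for strategy. For outcomes with a baseline, conditioning on it is at least as precise as change scores in large samples and removes the conditional bias from chance imbalance. At r = 0.5 the gain runs from a variance ratio of 1.33 (k = 1) to none (k = 0.5) for one follow-up, and a 0.3 SD imbalance mis-states the effect by 0.15 SD at k = 1 and 0.06 SD at k = 0.7. For follow-up-only outcomes the gain in precision is small.

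A reader might go further and infer that the WILLOW estimates are biased, or that a large loss of power has been shown. Neither follows. Change scores are not biased on average over randomisations when imbalance is due to chance, the documents give no baseline means, and they supply neither r nor k. Nor would adjustment fully remove differences that arise from recruitment after randomisation, knowledge of arm or the five-session rule. The unadjusted design effect is a separate matter that this change does not repair.

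**What to change.** 1. For patient outcomes with a baseline, model Weeks 4, 8 and 12 as responses, with the patient's own baseline score and its interaction with week as covariates, and report the Condition effect.
2. For follow-up-only outcomes, add the screening PHQ-9 total as a covariate, and say that little gain in precision is expected.
3. Remove the baseline significance tests as a basis for strategy. State which covariates, if any, the existing models contained.
4. Label the adjusted analyses as added after the fact and report them beside the Time by Condition and Condition results. Report the observed r and k, so that readers can see how much the choice matters.

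The cost is a revision of the SAP text and a re-run on data already collected, a few degrees of freedom, and a simple stated rule for patients with no baseline score.

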- You will be randomized to one of two conditions: the WILLOW condition or standard care condition.
- If you are randomized to the WILLOW condition, you will be asked to use a computer in session to guide you through conducting Behavioral Activation for the treatment of depression.
- If you are randomized to the standard care condition, you will be asked to conduct treatment as you normally would.
- In both cases, we will ask that you meet with 2-5 research patients for 12 weeks each. You can choose to treat as many study patients as your schedule allows. Patients that

WILLOW Full RCT Therapist Protocol

are enrolled in the study with you will need to be new patients to your clinic and must not have received treatment from you previously.

- You can still use WILLOW with your patients who are not involved in the research study.
- Participants in both conditions will be asked to complete one online survey before starting the study (baseline) and another set of online surveys with a brief telephone interview after 4, 8 and 12 weeks for each research patient they treat. You will be compensated \$50 for each 4 week and 8 week survey, and \$60 for each 12 week survey you complete.
- You will be eligible to obtain free access to WILLOW for 12 months after the completion of your participation, which involves successfully recruiting at least 1 study patient and completing all assessments for that patient.

Does this sound like something you would be interested in?

If no, thank them for their time and hang up.

If yes, proceed to the next section.

Awesome! The next step would be for you to read and sign a consent form.

The entire process takes about 15-20 minutes. I will send you an email shortly that contains the link to the consent form and we ask that you complete it within the next two days. After completing the consent form, we will randomize you to either the WILLOW condition or the standard care condition and follow up with orientation brief call to explain the next steps.

Do you have any last questions for me?

Thank you so much for your interest in our research. Please don't hesitate to contact us if you have any questions as you are reviewing the consent form. Have a great day!

Step 3: Send Consent Survey

1. Send therapist consent survey email
2. Log date consent sent in the [Summative Tracking DB](#)

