What if a crisis comes up and we don't get to BA that week - WILLOW is flexible – use your clinical judgment.

In addition to using it with your study patients, you can also choose to use WILLOW with your other patients who are not participating in the study. With those patients you can choose to use it however you like, whether you use the Behavioral Activation content or just the progress-monitoring feature. This means you can create WILLOW accounts for them or just print resources from WILLOW to use with them.

After your last study patient has completed their 12-trial for the research, you will then be given free So to be eligible to receive the free 12-month access to WILLOW after the research study, you must complete the study procedures for at least 1 study patient.

We just covered a lot of information! Do you have any questions so far?

Describe surveys (for both conditions):

We will ask for your feedback at various points in the study:

- **Describe Study surveys (for both conditions):** You have already completed your first set of surveys online. You will also be asked to complete surveys during Weeks 4, 8, and 12 for

WILLOW Full RCT Therapist Protocol

each of your patients. Surveys at Weeks 4 and 8 will consist of a brief phone interview and online survey. The phone interview will last approximately 10-15 minutes. You will be provided with a \$50 check that will be mailed to you for each week 4 and 8 survey you complete.

- The Week 12 surveys also consist of a phone interview and online survey. The phone interview will last about 30 minutes and the online survey will take another 30 minutes. You will be provided with a \$60 check for each week 12 survey you complete.
 - During your final study assessment, you will be asked to provide information about the exact number of sessions you conducted with each of your study patients.
 - In order to help you track these assessments, we will provide you with a session tracking sheet for your convenience.
- The checks will be coming from Chase Bank so be sure to keep your eyes out for an envelope from Chase when the time comes. It does often look like junk mail so we want to make sure that you're aware and not throwing those away.

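### Therapists are randomised, yet the SAP ignores clustering because design effects are below 2.0; at its own maximum of 1.8, a nominal 5% test has a false-positive rate of about 14%

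*SAP*

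**What the plan says.** **Unit of randomisation.** Therapist Protocol, Step 2 (Informed Consent Phone Call), tells the therapist: "You will be randomized to one of two conditions: the WILLOW condition or standard care condition". Step 5 describes the randomisation of that therapist. Patient Protocol, Step 3, tells the patient: "Your therapist has already been assigned to one of the two study conditions", and that the patient is therefore in the same condition. Condition never varies within a therapist.

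**Cluster size.** Therapist Protocol, Step 2, asks each therapist to take 2 to 5 study patients. Step 7 contemplates fewer: for free software access after the study, "you must complete the study procedures for at least 1 study patient". The SAP gives no achieved sizes and says only: "Several providers participated in the study concurrently with multiple patients".

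**Analysis.** The SAP (Analysis Strategy) fits a Generalized Linear Model in SPSS V19. It counts provider data by patients reported on, not by providers. Outcomes that have a baseline are tested by Time x Condition. For the others: "For outcomes measured only at follow-up points (e.g., therapeutic alliance and use of evidence-based therapy tasks), that was the Condition effects".

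**Clustering.** The SAP states: "Design effects ranged up to 1.8". It continues: "Because all were under 2.0, we did not adjust analyses to account for clustering effects", and cites one methods paper. It describes no mixed model, GEE, robust standard error or sensitivity analysis for clustering.

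**The concern.** When the cluster is also the randomised unit, all of the between-therapist variation falls on the comparison of arms. A patient-level analysis that treats records as independent then understates the variance of that comparison by the design effect. The SAP measured this understatement, found up to 1.8, and set it aside by means of a threshold that has no link to an error rate.

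Standard errors and confidence intervals are then too narrow and p-values too small for every outcome with positive clustering. Because only the maximum design effect is given, a reader cannot tell which reported differences would survive a correct analysis.

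**Working it through.** **Inputs.** Maximum design effect D = 1.8 and cut-off 2.0 (SAP, Analysis Strategy). Significance level: not stated, assumed two-sided 5%. Number of therapists, ICCs and achieved cluster sizes: not stated.

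**The plan's own figure.** The 1.8 cannot be reproduced, because its ingredients are not given. With equal clusters of m patients, D = 1 + (m − 1) × ICC, so 1.8 implies ICC = 0.8/(m − 1). That is 0.80, 0.40, 0.27 and 0.20 for m = 2, 3, 4 and 5. With small clusters, 1.8 means strong therapist effects.

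**Size of the error.** The true variance is D times the variance used, so the null rejection rate is 2 × [1 − Φ(1.96/√D)].

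| D | 1.96/√D | Null rejection rate |
|---|---|---|
| 1.2 | 1.789 | 7.4% |
| 1.5 | 1.600 | 11.0% |
| 1.8 | 1.461 | 14.4% |
| 2.0 (cut-off) | 1.386 | 16.6% |

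At D = 1.8:
- In WILLOW's favour alone, the rate is 7.2% against 2.5%.
- The standard error used is 1/√1.8 = 0.745 of the correct one, so it is 25% too small.
- Effective N is 1/1.8 = 56% of nominal.
- A nominal 95% interval covers 100% − 14.4% = 85.6%.
- An unadjusted p of 0.01 becomes 2 × [1 − Φ(2.576/√1.8)] = 0.055.
- To be a true 0.05, an unadjusted p must be 2 × [1 − Φ(1.96 × √1.8)] = 0.0085 or less.
- At other assumed levels, a nominal two-sided 1% becomes 5.5% and 10% becomes 22.0%.

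**Simulation check.** There were 20,000 null data sets per setting, with an assumed 15 therapists per arm, 2, 3 or 5 patients each, and the ICC set to give D = 1.8.

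| Test | Unadjusted rejection (m = 2 / 3 / 5) | On therapist means |
|---|---|---|
| Condition | 14.5 / 14.4 / 14.8% | 4.7 / 5.0 / 5.1% |
| Time x Condition, therapist effect constant over time | 4.9 / 5.1 / 4.9% | not needed |
| Time x Condition, D = 1.8 on change | 14.7 / 14.7 / 14.5% | 4.9 / 5.0 / 5.0% |

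Unequal clusters of 1 to 5 patients, singletons included (three assumed patterns), gave 14.4–14.8% for the unadjusted Condition test. Therapist means gave 4.9–5.1%, and CR2 standard errors with Satterthwaite degrees of freedom gave 5.2–5.5%. A separate simulation of the Condition test with 10, 20 or 40 therapists per arm and m = 2 to 5 gave unadjusted rates between 14% and 15%.

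**Which model corrects which test.** In four balanced data sets with baseline and one follow-up, random intercepts alone left the Time x Condition t statistic equal to the unadjusted one (for example 0.918 and 0.918). Adding a therapist-by-time effect reproduced the t statistic from therapist-mean change (0.667 and 0.667).

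**The case against.** The strongest objection concerns scope. The 1.8 is a maximum over outcomes, and the SAP does not say which outcome has it, whether it is provider- or patient-reported, or whether it was computed on levels or on change. For outcomes with a baseline, a therapist effect that is constant over time cancels from Time x Condition, and the simulation then shows no inflation. All of this stands. It limits where the 14.4% applies, but it does not rescue the rule: Condition-tested outcomes have no such cancellation, and the SAP names Condition as the effect of primary interest for them. Nor do therapist differences in how much patients change cancel.

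The figures for Time x Condition are for a single contrast. Patients are assessed at baseline and weeks 4, 8 and 12; if time is categorical the test has 3 degrees of freedom, and with 1.8 on every change contrast its large-sample rate is P(χ²₃ > 7.815/1.8), about 23%. The dependence on how time is coded is real, but this coding makes the problem larger.

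The SAP cites a methods paper for its cut-off. The arithmetic above follows from the meaning of a design effect and does not depend on that source.

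Two practical points also stand. A therapist-by-time effect may be poorly estimated with one to five patients per therapist. It has not been checked whether SPSS V19 offers CR2 standard errors. Finally, the SAP reads like an extract from a longer text, so cluster sizes and ICCs may exist elsewhere; the decision not to adjust would be unaffected.

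**Conclusion.** The concern holds. The 2.0 rule is wrong as written, because it permits a false-positive rate of up to 16.6% where 5% is intended. At the SAP's own maximum of 1.8 the rate is 14.4%, nearly three times nominal.

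That figure is a null rejection rate for the worst-affected outcome. It assumes a two-sided 5% level, a single-contrast test, and a design effect of 1.8 that refers to the effect tested. It is not an error rate for the trial as a whole. Confidence is high that the rule must go; how far each outcome is affected cannot be settled from the documents.

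**What to change.** Delete the rule that waives adjustment below 2.0, and account for therapist in every between-arm test:

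- **Condition-tested outcomes:** a mixed model with random intercepts for therapist and for patient within therapist.
- **Time x Condition outcomes:** the same, plus a therapist-by-time random effect, since intercepts alone do not correct that test.
- **Alternative for either:** cluster-robust standard errors by therapist with a small-sample correction (CR2 with Satterthwaite degrees of freedom). This is also a fallback where the therapist-by-time effect cannot be estimated stably.
- Base degrees of freedom on the number of therapists, and do not drop therapist terms because their estimates are small.
- State the significance level and sidedness. Report therapists per arm, achieved cluster sizes, and the ICC and design effect for each outcome, saying whether each is for level or change.

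**Cost.** SAP wording and a re-run on existing data, possibly in software other than SPSS V19. At D = 1.8, intervals widen by √1.8 − 1 = 34% from the variance alone. With therapist-level degrees of freedom the factor is √1.8 × t(0.975, 2k − 2)/1.96. This gives 37%, 40% or 44% for an assumed k = 30, 15 or 10 therapists per arm. At D = 1.2 the variance alone adds about 10%. The extra width is uncertainty that the data already carry and the current analysis does not show.
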